# 24. APPENDIX V. TOTAL BLOOD VOLUMES

An estimated 37.5 mL of blood will be collected for study assessments from each subject during the study as shown in Table 8.

**Table 8:** Blood Collection Volumes (mL)

Visit	1E	2E	3E	4E	5E	6E	7E	8E	9E	10E /ET	11E	12E	13E /EOS	
Week	Baseline	1	2	4	6	10	14	18	22	26	27	28	29	
Day (±3°)	0	7	14	28	42	70	98	126	154	182	189	196	203 (±7)	
Lab test														Total
Hematology	CO						2			2			2	6
Chemistry	CO						8.5			8.5			8.5	25.5
Thyroid Panel b	CO													
Lipid Panel b	CO													
Sex Hormone Tests	СО						2			2			2	6
Serum pregnancy (Females) a,b	СО													
TOTAL	0	0	0	0	0	0	12.5	0	0	12.5	1 60		12.5	37.5

Abbreviations: CO = Carried over from core study (no additional blood drawn; 0 mL), EOS = End of Study; ET = Early Termination = Visit.

 $a \ge 8$  years of age.

b Included in serum chemistry sample.

<sup>c Unless otherwise specified.

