12.2. LABORATORY EVALUATIONS

The following laboratory tests are planned to be performed:

HEMATOLOGY: (Differential reported as % and absolute value)

Hemoglobin, Hematocrit, Platelet Count, red blood cell (RBC) count, white blood cell (WBC) - total count, WBC differential reported as % and absolute values to include basophils, eosinophils, lymphocytes, monocytes, neutrophils.

BLOOD CHEMISTRIES:

Alanine aminotransferase (ALT), Alkaline Phosphatase (ALP), Aspartate aminotransferase (AST), Bicarbonate (HCO₃), Bilirubin (Total, Direct, Indirect), Blood Urea Nitrogen (BUN), Calcium (Ca), Chloride (Cl), Creatinine, Glucose, Magnesium

(Mg), Phosphorus (P), Potassium (K), Protein (Total), Sodium (Na), Uric Acid, Albumin

URINALYSIS:

Blood, Glucose, Ketones, Leukocyte Esterase, Microscopic Examination, Nitrites, pH, Protein

THYROID PANEL:

Free T3, Free T4, Thyroid stimulating hormone (TSH)

LIPID PANEL:

LDL-Cholesterol, HDL-Cholesterol, Total Cholesterol, Triglycerides

SEX HORMONES:

For females: estradiol, follicle-stimulating hormone (FSH), and luteinizing hormone (LH).

For males: testosterone.

URINE DRUG SCREENING:

Amphetamines, Barbiturates, Benzodiazepines, Cannabinoids, Cocaine, Methamphetamines, Methadone, Methylenedioxymethamphetamine (MDMA), Phencyclidine (PCP), Opiates, Oxycodone, Tricyclic Antidepressants

OTHER TESTS:

Breath Alcohol Test, Serum Pregnancy (B-hCG) (in female subjects only), Urine Pregnancy Test (in female subjects only)

Hematology, chemistry, urinalysis, thyroid panel, lipid panel, and sex hormones are collected at Open-label baseline, Week 14, Week 26 or ET, and the EOS Visit.

The laboratory results collected in conventional units will be converted to SI units, and the SI units will be used for all of the summaries and listings. Clinical laboratory test results (hematology, chemistry, urinalysis, thyroid panel, lipid panel, and sex hormones) and their changes from DB baseline and OL baseline will be summarized by DB treatment and overall, and by visits including the endpoint (Week 26 LOCF), using descriptive statistics. For hematology, chemistry lipid panel, thyroid panel, and sex hormone tests, result will also be categorized as “Normal”, “Low”, or “High” based on their normal ranges. For urinalysis results, tests will be classified as “Normal” or “Abnormal”. Shift tables comparing laboratory test results from baseline to Week 26

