LOCF will be presented. Percentages are based on the number of the safety subjects in a high, low or normal category with non-missing values for both baseline and post-baseline at the given visit.

In addition, the markedly abnormal post-baseline laboratory results will be summarized for certain laboratory tests.

Summaries will be presented separately for hematology and chemistry for subjects with at least one markedly abnormal value during the open-label treatment period. A listing of all markedly abnormal results will be provided.

The criteria for markedly abnormal values are defined below.

Parameter (Unit)	Markedly Abnormal Range (Conventional Unit)	Conversion Factor (Conventional to SI) / SI unit	SI Unit Markedly Abnormal Range
Hematology			
Hemoglobin (g/dL)	Female: ≤ 9.5, Male: ≤ 11.5 ≥ 17.2	10 / g/L	Female: ≤ 95 g/L, Male: ≤ 115 g/L, ≥ 172 g/L
Hematocrit (fraction, %)	≤ 30, ≥ 50	0.01 / (fraction of 1)	≤ 0.30, ≥ 0.50 (1)
WBC (10 ³ /μL)	≤ 2.8, ≥ 16	1 / x10 ⁹ /L (PPD Conv unit K/cu mm)	≤ 2.8, ≥ 16
RBC (10 ⁶ /μL)	≤ 3.0, ≥ 6.0	1 / x10 ¹² /L (PPD Conv unit x10 ⁶ /cu mm)	≤ 3.0, ≥ 6.0
Platelet Count (10 ³ /μL)	≤ 100, ≥ 500	1 / x10 ⁹ /L (PPD Conv unit K/cu mm)	≤ 100, ≥ 500
Eosinophils (%)	≥ 10	1 / %	≥ 10

Parameter (Unit)	Markedly Abnormal Range (Conventional Unit)	Conversion Factor (Conventional to SI) / SI unit	SI Unit Markedly Abnormal Range
Neutrophils (%)	≤ 15	1 / %	≤ 15
Clinical Chemistry			
ALP (U/L)	≥ 3 x ULN	1 / U/L	≥ 3 x ULN
ALT (U/L)	≥ 2 x ULN	1 / U/L	≥ 2 x ULN
AST (U/L)	≥ 2 x ULN	1 / U/L	≥ 2 x ULN
Total Bilirubin (mg/dL)	≥ 2.0	17.1 / μmol/L	≥ 34.2
Albumin (g/dL)	< 50% LLN	10 / g/L	< 50% LLN
Creatinine (mg/dL)	≥ 2.0	88.4 / μmol/L	≥ 176
Creatine Phosphokinase (CPK) (U/L)	≥ 450	1 / U/L	≥ 450
LDH (U/L)	≥ 3 x ULN	1 / U/L	≥ 3 x ULN
GGT (U/L)	≥ 150	1 / U/L	≥ 150
Sodium (mEq/L)	≤ 130, ≥ 150	1 / mmol/L	≤ 130, ≥ 150
Potassium (mEq/L)	≤ 3, ≥ 5.5	1 / mmol/L	≤ 3, ≥ 5.5
Bicarbonate (mEq/L)	< 18, > 30	1 / mmol/L	< 18, > 30
Calcium (mg/dL)	< 8.4, or > 11.5	0.25 / mmol/L	< 2.1, or > 2.8

Parameter (Unit)	Markedly Abnormal Range (Conventional Unit)	Conversion Factor (Conventional to SI) / SI unit	SI Unit Markedly Abnormal Range
Chloride (mEq/L)	< 90, > 115	1 / mmol/L	< 90, > 115
Blood Urea Nitrogen (mg/dL)	≥ 30	0.357 / mmol/L	> 10.7
Glucose (fasting) (mg/dL)	≤ 45, ≥ 126	0.05551 / mmol/L	≤ 2.5, ≥11.1
Glucose (random) (mg/dL)	≤ 45, > 200	0.05551 / mmol/L	≤ 2.5, ≥11.1
Lipid Panel (Fasting)			
Total Cholesterol (mg/dL)	≥ 240	0.0259 / mmol/L	≥ 6.2

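### The fasting glucose row in SAP 12.2 contradicts itself: 126 mg/dL converts to 6.99 mmol/L, but the SI cut-off is printed as 11.1 mmol/L

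*SAP*

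**What the plan says.** SAP Section 12.2 (Laboratory Evaluations) has a table that defines the markedly abnormal criteria. Each row gives a limit in conventional units, a conversion factor and a limit in SI units. The two glucose rows are:

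- fasting: "Glucose (fasting) (mg/dL) ≤ 45, ≥ 126 0.05551 / mmol/L ≤ 2.5, ≥11.1"
- random: "Glucose (random) (mg/dL) ≤ 45, > 200 0.05551 / mmol/L ≤ 2.5, ≥11.1"

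The same section says that results in conventional units are converted and that "the SI units will be used for all of the summaries and listings". It does not say whether the conventional or the SI column sets the flag.

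The criteria feed two outputs. One is a summary of subjects "with at least one markedly abnormal value during the open-label treatment period". For the other, the SAP says: "A listing of all markedly abnormal results will be provided".

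On timing, the SAP says that chemistry and the other panels "are collected at Open-label baseline, Week 14, Week 26 or ET, and the EOS Visit". Protocol Sections 11.4.7, 11.4.10 and 11.4.11.3 ask for at least 8 hours of fasting before the lipid panel draw at Week 14, Week 26/ET and Week 29. Protocol Appendix V, Table 8 footnotes the lipid panel as "Included in serum chemistry sample", and the SAP heads the lipid rows "Lipid Panel (Fasting)".

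**The concern.** The two glucose rows have different upper limits in mg/dL (126 and 200) but the same upper limit in mmol/L. As printed, the distinction between fasting and random glucose disappears in SI units, and the fasting cell looks like a copy of the cell below it.

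The direction of the error matters. Under the SI column the table under-reports: a fasting value that meets the conventional criterion is left out of the markedly abnormal count and listing, and nothing in those outputs would show that it was missing. Clinical laboratory evaluations are a secondary endpoint of a study whose purpose is long-term safety in children. The fasting row is also the one expected to apply at the scheduled post-baseline draws, because glucose and lipids come from the same sample and subjects are asked to fast for it.

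**Working it through.** Inputs, all from the SAP 12.2 table: fasting limits 45 and 126 mg/dL; random upper limit 200 mg/dL; factor 0.05551; printed SI limits 2.5 and 11.1 mmol/L.

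Formula: SI limit = conventional limit × factor.

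**Cells that reproduce**

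- Lower limit, both rows: 45 × 0.05551 = 2.498, printed 2.5.
- Random upper limit: 200 × 0.05551 = 11.102, printed 11.1.

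**The cell that does not**

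- Fasting upper limit: 126 × 0.05551 = 6.994, printed 11.1.
- Ratio: 11.1 / 6.994 = 1.587, so the printed limit is 59% too high.
- Back-conversion: 11.1 / 0.05551 = 199.96 mg/dL.

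**Values caught between the columns**

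- 199 × 0.05551 = 11.046, below 11.1; 200 × 0.05551 = 11.102, above it.
- Whole values from 126 to 199 mg/dL therefore meet the conventional limit and fail the SI limit: 199 − 126 + 1 = 74. The count is the same if SI values are unrounded, or rounded to two decimals or to one.

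**Is it rounding?** The other rows with numeric limits and a factor other than 1 were converted in the same way. The largest gap elsewhere is 2.6%.

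| Row (upper limit unless stated) | Conventional × factor | Printed SI | Gap |
|---|---|---|---|
| Fasting glucose | 126 × 0.05551 = 6.994 | 11.1 | +58.7% |
| Calcium | 11.5 × 0.25 = 2.875 | 2.8 | −2.6% |
| HDL (lower limit) | 30 × 0.0259 = 0.777 | 0.77 | −0.9% |
| Creatinine | 2.0 × 88.4 = 176.8 | 176 | −0.5% |
| Total cholesterol | 240 × 0.0259 = 6.216 | 6.2 | −0.3% |

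The rest are within 0.1%. Rounding does not explain the fasting glucose cell.

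**Small mismatches in the same column, on unrounded values**

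- Calcium: 2.8 / 0.25 = 11.2 mg/dL, so 11.3, 11.4 and 11.5 mg/dL would be flagged although the conventional limit is > 11.5.
- HDL: 30 mg/dL gives 0.777, above 0.77, so it would be missed although the conventional limit is ≤ 30.
- Random glucose: 200 mg/dL gives 11.102 and would be flagged under ≥ 11.1, although the conventional limit is > 200.

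**Check of the replacement, on unrounded values**

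- ≥ 6.99: 125 × 0.05551 = 6.939 (not flagged) and 126 × 0.05551 = 6.994 (flagged). No mismatch with ≥ 126 mg/dL.
- ≥ 7.0: 6.994 is below it, so exactly 126 mg/dL would be missed.

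**The case against.** The arithmetic is not in dispute. The case against concerns its reach.

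- **Which column governs.** The SI statement in SAP 12.2 sets the reporting unit. A programmer could apply the conventional limits before conversion and stay within the text, and then nothing is missed. This stands: the loss of flags is conditional. The contradiction is not, and two programmers working from this table could report different counts.
- **Which row applies.** The fasting instruction is written for the lipid panel. The SAP has no rule for classing a glucose result as fasting or random, and the protocol's visit lists name no recording of fasting status. This also stands. It limits what can be said about how many values are affected, and correcting the cell alone would not settle it.
- **Other safeguards.** Out-of-range results go to the investigator, and clinically significant ones after dosing are recorded as adverse events (Protocol 12.2). The descriptive statistics do not use this cut-off, and the shift tables use the laboratory's normal ranges. The primary endpoint is adverse event incidence. All of this is true, and it confines the effect to one flag count and one listing.
- **Intent.** The documents do not say which cell was meant. The row's own factor, its correct lower limit and the separate 126 and 200 limits all favour the conventional cell, but the sponsor should confirm this.

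**Conclusion.** The concern holds and should be fixed. The upper SI limit for fasting glucose is wrong by the row's own factor: 11.1 against 6.99 mmol/L, 59% too high. No other text in the protocol or SAP corrects it.

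The consequence rests on two assumptions: that the SI column sets the flag, which is likely but not stated, and that scheduled post-baseline glucose values are treated as fasting, which the protocol's instructions suggest but the SAP does not specify. Under both, fasting values of 126 to 199 mg/dL would be absent from the markedly abnormal chemistry summary (Week 14 and Week 26/ET draws) and from the listing (Week 29 as well). No data are lost, and the number of subjects affected cannot be computed from the documents. The calcium, HDL and random glucose mismatches are minor.

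**What to change.** 1. Reconcile the two fasting cells. If the sponsor confirms the conventional limit, set the SI upper limit to the row's own conversion, ≥ 6.99 mmol/L.
2. Add one sentence stating that the SI limits set the flag and are applied to unrounded SI values. Alternatively, state that flags are set on the conventional values before conversion; that would remove every conversion mismatch in the table, but the printed SI cells should still be corrected.
3. If the SI column is kept as the criterion, correct three minor cells in the same pass: calcium upper limit > 2.875, HDL ≤ 0.777, random glucose > 11.102. Changing only the sign of the random glucose limit to > 11.1 would still flag 200 mg/dL.
4. State how a glucose result is assigned to the fasting or the random row.

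The cost is one cell for the main error, three minor cells and two sentences in the SAP. No new data are needed for the corrected limits. More fasting glucose values and fewer calcium values may be flagged as a result.

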12.3. BREATH ALCOHOL TEST

Breath alcohol examination will be monitored at Open-Label Baseline, Week 14, and the EOS Visit. The breath alcohol examination data will be presented in a data listing.

12.4. URINE DRUG SCREENING

Urine drug screening tests are collected at Open-Label Baseline, Week 2, Week 6, Week 10, Week 14, Week 18, Week 22, Week 26, and at the EOS. The urine drug screening data will be presented in a data listing.

12.5. 12-LEAD ECG

Assessment of Standard 12-lead ECG are obtained at each clinic assessment during the study. A central ECG Standard 12-lead ECG will record heart rate (HR), PR interval, RR interval, QT interval, Bazett's corrected QT (QTcB), Fridericia's corrected QT interval (QTcF), and QRS duration. The overall ECG assessment will be centrally reported as "Normal", "Abnormal, Not Clinically Significant", or "Abnormal, Clinically Significant" with respect to relevant abnormalities.

Observed results of each ECG parameter, change from DB baseline, and change from OL baseline will be summarized by DB treatment and overall, and by visit using descriptive statistics.

The QTcF and QTcB results will be adjusted as follows:

$$QTcF = QT / \sqrt[3]{RR}$$

$$QTcB = QT / \sqrt[2]{RR}$$

Bazett's and Fridericia's corrected QT_c values will be classified as having QT_c prolongation according to the following conditions.

QTc Prolongation
QTc >460 msec

QTc Prolongation
Increase from double-blind baseline QTc \geq 60 msec
Increase from double-blind baseline QTc \geq 30 msec
Increase from open-label baseline QTc \geq 60 msec
Increase from open-label baseline QTc \geq 30 msec

The number and percentage of subjects with QTc prolongation using either of the two correction methods (Bazett's, Fridericia's) will be summarized by DB treatment and overall, and by visit.

A shift table comparing the overall ECG assessment from baseline to Week 26 or ET, and from baseline to EOS will be presented.

In addition, the markedly abnormal post-baseline ECG results will also be summarized for subjects with at least one markedly abnormal value during the treatment period. The summary will be completed by DB treatment and overall, and age groups (6 - < 8 years, 8 - < 12 years, 12 - < 16 years, and > 16 years), and overall using the age at the time of the individual assessment.

A listing of markedly abnormal values will be provided.

Criteria for markedly abnormal values, used in the SEP360-202 study, are presented in the table below. They will also be used for the SEP360-310 study summary.

ECG parameter (unit)	Age (years old)	Abnormally Low	Abnormally High
HR (bpm)	6 to <8	< 65	> 115
	8 to <12	< 55	> 110
	12 to <16	< 50	> 105
	\geq 16	< 50	> 100
PR interval (msec)	6 to <8	--	> 160
	8 to <12	--	> 175
	12 to <16	--	> 180
	\geq 16	--	> 200
QRS interval (msec)	6 to <8	--	> 100
	8 to <12	--	> 105

ECG parameter (unit)	Age (years old)	Abnormally Low	Abnormally High
	12 to <16	--	> 110
	≥16	--	> 120

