- Data for unscheduled assessments will be included when selecting worst result for shift analyses, and for summary of normal/abnormal values. The summary of observed value and change from DB baseline and change from OL baseline data will be performed by nominal visits (scheduled visits). Unscheduled assessments will be included in Week 26 or Treatment Period LOCF, as long as that unscheduled assessment was not completed more than 3 days after the last dose of study medication.

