12.7. NEUROLOGICAL EXAMINATION

Neurological examinations will be performed at Open-Label Baseline, Week 14, Week 26 or ET, and End of Study.

Each assessment (i.e. Cranial Nerves, Motor System, Sensory System, Reflexes, Coordination, Gait and Romberg's test) will be summarized using summary statistics for categorical variables (normal/abnormal) at each visit by treatment and overall. All percentages will be based on the number of safety subjects in each DB treatment group.

Shift table for baseline condition vs. the worst result during the treatment period (Abnormal > Normal) will be produced by DB treatment and overall. Percentages will be based on the number of subjects in the safety population. The number of subjects without an assessment at the visit will be noted on the shift table.

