12.8. VITAL SIGNS

Vital signs (blood pressure, pulse rate, height, height WHO z-score, weight, BMI, BMI z-score, respiratory rate, and oral temperature) will be monitored at every clinic visit. Respiratory rate and oral temperature will be measured following 5 minutes of supine rest.

At any clinic assessment, orthostatic hypotension (determined by blood pressure measurements only) is defined as having either a ≥ 20 mmHg reduction from supine to standing position in systolic blood pressure (SBP) or ≥ 10 mmHg reduction from supine to standing position in diastolic blood pressure (DBP) or both. Orthostatic tachycardia is defined as heart rate increase ≥ 20 bpm from supine to standing position.

Observed values, change from DB baseline, percent change from DB baseline, change from OL baseline, percent change from OL baseline for each vital sign parameter. will be summarized at each visit by DB treatment and overall.

In addition, the markedly abnormal post-baseline vital signs results will also be summarized for subjects with at least one markedly abnormal value during the treatment period. A listing will be provided for all markedly abnormal vital signs. A shift table will be presented comparing shifts from the baseline visit to Week 26 LOCF. Percentages will be based on the number of safety subjects with a non-missing value for both the baseline and post-baseline visit for the given vital sign. A shift table for BMI classification will also be presented comparing shifts from the baseline visit to Week 26 LOCF.

Parameter (unit)	Age (years old)	Markedly Low	Markedly High
SBP (supine, standing) (mmHg)	6-12	Value ≤ 70 and ≥ 20 decrease from baseline	Value ≥ 120 and ≥ 20 increase from baseline
	13-18	Value ≤ 90 and ≥ 20 decrease from baseline	Value ≥ 135 and ≥ 20 increase from baseline
DBP (supine, standing) (mmHg)	6-12	Value ≤ 40 and ≥ 15 decrease from baseline	Value ≥ 80 and ≥ 15 increase from baseline
	13-18	Value ≤ 50 and ≥ 15 decrease from baseline	Value ≥ 90 and ≥ 15 increase from baseline
Pulse rate (supine, standing) (bpm)	6-10	Value ≤ 60 and ≥ 15 decrease from baseline	Value ≥ 135 and ≥ 15 increase from baseline
	11-18	Value ≤ 50 and ≥ 15 decrease from baseline	Value ≥ 120 and ≥ 15 increase from baseline
SBP orthostatic criteria (mmHg)	~	≥ 20 decrease from supine to standing position	NA
DBP orthostatic criteria (mmHg)	~	≥ 10 decrease from supine to standing position	NA

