12.9. Columbia-Suicide Severity Rating Scale (C-SSRS)

The Columbia-Suicide Severity Rating Scale (C-SSRS) is a questionnaire used for suicide assessment that evaluates suicidal ideation and behavior.

This study will utilize the “Since Last Visit” version of the C-SSRS at each visit.

Subjects will be placed into categories for suicidal ideation and for suicidal behavior based on their responses to various questions.

The Suicidal Ideation categories will be determined as follows by examining the response to the 5 questions under Suicidal Ideation.

Type	Section
Suicidal Ideation	
(0) None - if response is No to Questions 1 and 2
 
(1) Wish to be Dead - if response to Question 1 is Yes and responses to Questions 2-5 are No.
 
(2) Non-Specific Active Suicidal Thoughts - if response to Question 2 is Yes and response to Questions 3-5 are No.
 
(3) Active Suicidal Ideation with Any Methods (Not Plan) without Intent to Act - if response to question 3 is Yes and response to questions 4 and 5 are No.
 
(4) Active Suicidal Ideation with Some Intent to Act, without Specific Plan - if response to Question 4 is Yes and response to Question 5 is No.
 
(5) Active Suicidal Ideation with Specific Plan and Intent - if response to Question 5 is Yes.

For suicidal behavior, the following categories will be used. The categories will be determined based on the response to the questions under Suicidal Behavior.

Type	Section
Suicidal Behavior	
 • Preparatory Acts or Behavior - if response to Preparatory Acts and Behavior is Yes and responses to Actual Attempt, Interrupted Attempt, and Aborted Attempt are No • Aborted Attempt - if response to Aborted Attempt is Yes and responses to Actual Attempt and Interrupted Attempt are No. • Interrupted Attempt - if response to Interrupted Attempt is Yes and response to Actual Attempt is No. • Actual Attempt - if response to Actual Attempt is Yes. • None - if responses to all the above 4 questions are No.

The frequency and percentage by DB treatment and overall, and visit will be summarized for all C-SSRS responses.

Frequency and severity of suicidality using the C-SSRS will be summarized, using a shift table to examine changes in C-SSRS Scores from baseline compared to the worst (highest) category during the treatment period and visit, by DB treatment and overall.

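### The laboratory, vital-sign, BMI-class and overall ECG shift tables use only end-point values, so an abnormality that resolves on treatment is missing from them, and several measures have no other any-time table.

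*SAP*

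**What the plan says.** Four shift displays use fixed end points:

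- **Laboratory (SAP 12.2):** "Shift tables comparing laboratory test results from baseline to Week 26"; the sentence goes on to specify LOCF.
- **Vital signs (SAP 12.8):** "A shift table will be presented comparing shifts from the baseline visit to Week 26 LOCF". The BMI-class shift has the same end point.
- **Overall ECG assessment (SAP 12.5):** "A shift table comparing the overall ECG assessment from baseline to Week 26 or ET, and from baseline to EOS will be presented". The EOS visit is about three weeks after the final dose (Protocol 7.1).

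Two shift displays use the worst value:

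- **Neurological examination (SAP 12.7):** "Shift table for baseline condition vs. the worst result during the treatment period (Abnormal > Normal) will be produced by DB treatment and overall".
- **C-SSRS (SAP 12.9):** changes "from baseline compared to the worst (highest) category during the treatment period and visit".

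The general rule in SAP 6.1 reads: "Data for unscheduled assessments will be included when selecting worst result for shift analyses, and for summary of normal/abnormal values".

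The protocol's statistics section (15.3.6.2 and 15.3.6.4) asks for laboratory and vital-sign shifts from baseline to end of study. It does not ask for a worst-value shift for either.

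**The concern.** Dosing is flexible. Protocol 7.1 and 10.2 let the investigator reduce the dose for tolerability, with no limit on the number of reductions. A child can therefore have an abnormal finding, have the dose lowered, recover and stay in the study. In a shift table that ends at the last on-treatment value, that child is counted as normal to normal. The EOS column of the ECG table does not help, because by then the child is off drug.

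The primary objective is long-term safety, and laboratory results, vital signs and ECG are named secondary endpoints. A reader of the report will want to know how many children were abnormal at any time on treatment. For some measures, no table specified in the SAP text answers that.

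**Working it through.** **Step 1. Where a transient on-treatment abnormality would appear, apart from the shift table.**

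| Measure | Other output specified | Any-time subject count? |
|---|---|---|
| Hematology and chemistry, marked values | Treatment-period summary and listing (SAP 12.2) | Yes |
| ECG HR, PR, QRS, marked values | Treatment-period summary and listing (12.5) | Yes |
| Blood pressure, pulse, temperature, marked values | Treatment-period summary and listing (12.8) | Yes |
| QTc prolongation | Count by visit (12.5) | No |
| Overall ECG category | None beyond the shift | No |
| Lipids, urine RBC/WBC, FSH, LH | Marked criteria exist; listing assured | Not clearly |
| Thyroid tests, estradiol, testosterone | No marked criteria; by-visit statistics | No |
| Low/High or abnormal laboratory values short of a marked threshold | By-visit statistics | No |
| BMI class | No marked criteria for weight or BMI; by-visit BMI statistics | No |

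The lipid, urinalysis and FSH/LH row is uncertain because SAP 12.2 names only two panels for the treatment-period table: "Summaries will be presented separately for hematology and chemistry for subjects with at least one markedly abnormal value during the open-label treatment period". A more general sentence just before it promises a summary of marked results for certain tests, without saying which.

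**Step 2. How much of the treatment period each shift uses.** By the schedule of assessments, ECG and vital signs are taken at Weeks 1, 2, 4, 6, 10, 14, 18, 22 and 26, which is nine scheduled on-treatment assessments. Laboratory panels are taken at Weeks 14 and 26, which is two. The shift uses one of nine and one of two respectively.

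**Step 3. Illustration of size.** The documents give no abnormality rate, so there is no plan figure to reproduce. Assumptions: the same rate p at every visit, no dropout and N = 330 (the projected maximum). With k independent visits:

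- Probability of being abnormal at least once = 1 − (1 − p)^k
- Share of ever-abnormal children not abnormal at the last visit = 1 − p / [1 − (1 − p)^k]

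At p = 2%:

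- **ECG, k = 9:** 1 − 0.98^9 = 0.166, about 55 of 330 children ever abnormal, against 0.02 × 330 = 6.6 at the last visit. Share not shown = 1 − 0.02/0.166 = 88%.
- **Laboratory, k = 2:** 1 − 0.98² = 0.0396, about 13 children, against 6.6. Share not shown = 1 − 0.02/0.0396 = 49.5%, about half.

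Varying p from 0.5% to 5% under independence gives 89% down to 86% for ECG and about 50% down to 49% for laboratory.

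Abnormalities usually persist to some degree within a child. With p = 2% and a probit random-effect model (latent within-child correlation ρ):

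| ρ | ECG (9 visits), not shown | Laboratory (2 samples), not shown |
|---|---|---|
| 0 | 88% | 50% |
| 0.3 | 85% | 48% |
| 0.6 | 80% | 43% |
| 0.9 | 61% | 30% |
| Fully persistent | 0% | 0% |

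These shares describe one shift table, not the whole report.

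**The case against.** The case for leaving the plan alone has real substance.

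- **Other outputs catch much of this.** A reader might infer that resolved abnormalities disappear from the report. They do not. Marked values are summarized or listed, QTc prolongation is tabulated at each visit, laboratory values are summarized by visit (so Week 14 is visible in aggregate), and all safety data are listed by subject and visit (SAP 12). Under Protocol 12.2 the investigator reviews the ECG over-reads and out-of-range laboratory values, and clinically significant findings are recorded as AEs, whose incidence is the primary endpoint. This stands, with one limit: SAP 12.5 takes the ECG category from the central reading, while AE recording follows the investigator's judgement. A centrally abnormal ECG need not become an AE, particularly if it is read as not clinically significant.
- **SAP 6.1 is not contradicted.** It is tempting to read its sentence on unscheduled data as requiring the worst value in every shift table. It says only that unscheduled data count where a worst result is selected, as in 12.7 and 12.9. The same section describes shifts as baseline against post-baseline at a given visit, so both kinds of table fit it.
- **The protocol asked for a last-value comparison.** It specifies end of study for laboratory and vital signs, and the SAP implements an end-of-treatment version. That is a reason to keep these tables, but it does not bar an added one.
- **Children who stop treatment early are largely covered.** LOCF admits early-termination and unscheduled values up to three days after the last dose, so a child who stops because of an abnormality would usually still show it. The gap concerns children who recover and continue.
- **The table shells are not available.** Any statement that a table is absent is limited to the SAP text.

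**Conclusion.** The point holds as a reporting gap. The laboratory, vital-sign, BMI-class and overall ECG shift tables cannot show an abnormality that resolves before the last on-treatment value. For the overall ECG category, QTc prolongation, thyroid tests, estradiol, testosterone, laboratory values short of a marked threshold and BMI class, the SAP text specifies no any-time subject-level table in their place. For lipids, urine RBC/WBC and FSH/LH only the listing is clearly assured.

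The size is unknown. The range of 0% to about 88% (ECG) or about 50% (laboratory) rests on an assumed constant 2% rate, no dropout and the two extremes of persistence. It shows what the table could miss and is not an estimate of under-reporting in this trial. The data are collected and listed, so nothing is irrecoverable. The documents do not support a claim that safety findings are lost, that the SAP breaks its own rule, or that the existing shifts are wrong.

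**What to change.** Keep the Week 26 LOCF, Week 26/ET and EOS shifts. Add beside them, in SAP 12.2, 12.5 and 12.8:

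1. A shift from baseline to worst on-treatment value, using scheduled and unscheduled assessments up to three days after the last dose, for the laboratory panels, the overall ECG category, vital signs and BMI class. For two-sided laboratory tests, show worst-low and worst-high separately.
2. A count of subjects with QTc prolongation at any time on treatment, for each criterion already listed in 12.5.

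The cost is a few extra tables with their programming and SAP wording. No new data or change to visits is needed.
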